11 STATISTICS AND DATA ANALYSES

11.1 Statistical Design

The study is an Observational Non-randomised Phase 2 study to determine the magnitude of change in [¹⁸F]FPIA-detectable SCFA uptake in mRCC using [¹⁸F]FPIA PET/CT following therapy. This is the first time we are using [¹⁸F]FPIA in patients with mRCC, thus we do not know *a priori* the magnitude of uptake. Statistical tests will use a 0.05 significance level and will be 2-sided unless otherwise noted. 24 evaluable patients will be recruited for the study with the Upper Confidence Interval of sensitivity to detect [¹⁸F]FPIA-detectable SCFA uptake set to $\geq 90\%$.

11.2 Data Analysis

The clinical data will be entered and stored in an appropriate database. An early stage review of tracer uptake after 5 cases will be carried out. A final analysis will be conducted at the end of the study.

The data analysis will consist of completed cases, i.e. all patients who completed the [¹⁸F]FPIA scans and 12 weeks (\pm 4 weeks) of therapy. This is because the primary endpoint of change in uptake of [¹⁸F]FPIA from baseline is measured based on the PET/CT scans pre- and post- therapy.

Analysis of the imaging data will be quantified using SUV. The whole body scans will provide response information (change in SUV) on non-target and target lesions combined. Regions of interest (ROIs) corresponding to tumour and healthy tissue will be drawn on PET images and used to derive semi-quantitative uptake parameters. These may include SUVmean (mean of standardized uptake values (SUV) within an ROI) normalised to body weight (bw), SUVmax and SUVpeak; tumour to background ratio.

The analysis will be reviewed by an experienced investigator/ radiologist/ statistician.

The following associations will be determined: between PET and biological measures

- The relationship between PET and cell proliferation determined by histology.
- The relationship between PET and biological drivers of fatty acid metabolism determined by histology.

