4 STUDY OBJECTIVES AND ENDPOINTS

4.1 Primary:

Primary Objective	Primary Endpoint
Determine the magnitude of change in [¹⁸ F]FPIA-detectable SCFA uptake in mRCC following therapy.	Quantitative longitudinal measurement of [¹⁸ F]FPIA uptake in mRCC.

4.2 Secondary:

Secondary Objectives	Secondary Endpoint
To determine how [¹⁸ F]FPIA-detectable SCFA uptake in healthy tissue compares to tumour.	Quantitative measurement of FPIA in healthy tissue including kidneys.
To determine if changes in [¹⁸ F]FPIA-detectable SCFA uptake in mRCC at 4-6 weeks and at 12 weeks (± 4 weeks) are related to routinely measured imaging changes.	Comparison of [¹⁸ F]FPIA relative to baseline at 4-6 weeks and at 12 weeks (± 4 weeks) to changes on a patient's routine imaging scan e.g. CT chest-abdo-pelvis, Whole body FDG-PET, ultrasound or MRI (RECIST 1.1 or irRECIST or PERCIST).

4.3 Tertiary:

Tertiary Objective	Tertiary Endpoint
To investigate if baseline or changes in [¹⁸ F]FPIA-detectable SCFA uptake in mRCC correlate with mutational signature.	[¹⁸ F]FPIA uptake versus Tumour Mutational Burden (TMB) on biopsy material.
To investigate if baseline or changes in [¹⁸ F]FPIA-detectable SCFA uptake in mRCC correlate with serum or urine carnitine/carnitine ester signature.	[¹⁸ F]FPIA uptake versus serum or urine carnitine/carnitine ester signature.

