5.2 Study Flow Chart

6 PARTICIPANT ENTRY

[figure not shown]
A target of 24 evaluable subjects will be recruited.

In the event of withdrawals or non-evaluable data before or after dosing, additional subjects will be recruited to reach a total number of 24 evaluable subjects. Evaluable data from patients who drop out will be used whenever possible.

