8.2 Rules for subject withdrawal

There are no formal withdrawal criteria for this study. During the conduct of the study, the study team will review the safety data for trends and signals that would indicate the need for withdrawal of a subject.

In accordance with the Declaration of Helsinki, each subject is free to withdraw from the study at any time. Investigator(s) also have the right to withdraw subjects from the study in the event of illness, AEs, or other reasons concerning the health or well-being of the subject, or in the case of lack of co-operation. Should a subject decide to withdraw after administration of the tracer, or should the investigator decide to withdraw the subject, all efforts will be made to complete and report the observations up to the time of withdrawal as thoroughly as possible. A complete final evaluation at the time of the

subject's withdrawal will be made and an explanation given of why the subject is withdrawing or being withdrawn from the study.

Subjects who discontinue standard of care treatment before scan visit 2 will not proceed to scan 2 or scan 3.

Subjects who discontinue standard of care treatment between scan visit 2 and scan visit 3 will be reviewed by the investigator with regard to proceeding to scan visit 3 depending on proximity of treatment cessation to final scan window.

The reason for non-completion and the date and time of the last contact with the subject must be noted in the research documentation. If the reason for withdrawal is a clinical AE or an abnormal laboratory result, monitoring will continue until the outcome is evident. The specific event or test result(s) must be recorded in the research documentation.

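### Section 11.2 limits the analysis to completers for a reason that does not require it, and this conflicts with the promise in section 6 to use drop-out data

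*Combined protocol and SAP*

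**What the plan says.** Section 11.2 sets one analysis population: "The data analysis will consist of completed cases, i.e. all patients who completed the" [18F]FPIA scans together with 12 (±4) weeks of therapy. The reason it gives is that the primary endpoint, change from baseline, "is measured based on the PET/CT scans pre- and post- therapy". No endpoint or visit is exempted, and no other analysis set is named.

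Section 6 says: "Evaluable data from patients who drop out will be used whenever possible". Section 8.2 says that when a subject is withdrawn after tracer administration, "all efforts will be made to complete and report the observations up to the time of withdrawal as thoroughly as possible".

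Section 8.2 also foresees incomplete scan sets. "Subjects who discontinue standard of care treatment before scan visit 2 will not proceed to scan 2 or scan 3". Those who stop between scans 2 and 3 "will be reviewed by the investigator with regard to proceeding to scan visit 3".

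Section 4 gives the primary endpoint as longitudinal uptake and names no single visit. The secondary endpoints compare uptake "relative to baseline at 4-6 weeks and at 12 weeks" (±4 weeks) with routine imaging, and include "Quantitative measurement of FPIA in healthy tissue including kidneys". The tertiary objectives relate baseline uptake, or its change, to tumour mutational burden (TMB) and to carnitine.

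Sections 5.1, 8.1.1 and 8.1.2 define complete and evaluable by scans and image quality, with no condition on therapy duration.

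**The concern.** The restriction is wider than its reason. Requiring a scan before and a scan after therapy does not exclude a patient who has baseline and scan 2, and it has no bearing on an objective that can be met from the baseline scan. Section 6 says such data will be used, but section 11.2 admits no analysis that would use them.

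Two things are at stake. Measurements already taken may be left out of a study planned around only 24 evaluable patients. Also, completing the schedule happens after treatment starts, and the hypothesis in section 3.2 is that uptake falls with effective treatment. If staying in the study is related to that fall, the completer mean is not the mean change after starting therapy. Replacing drop-outs restores the count of 24 but does not make the completers representative.

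**Working it through.** **1. Objectives against the restriction**

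| Objective (section 4) | Scans needed | Admitted by 11.2 |
|---|---|---|
| Change at 4-6 weeks, and its relation to routine imaging | 1 and 2 | Completers only |
| Change at 12 (±4) weeks, and its relation to routine imaging | 1 and 3 | Completers only |
| Healthy tissue against tumour | Can use 1 alone | Completers only |
| Baseline uptake against TMB and carnitine | 1 | Completers only |

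Only the second row needs scan 3. Under section 8.2, patients who stop therapy before scan 2 have a baseline scan only. Some who stop between scans 2 and 3 will have scans 1 and 2 only.

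**2. Precision, assuming no bias**

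The documents give no drop-out rate, effect size or SD for uptake change, so the plan has no figure of its own to reproduce here. The basis for 24 is a separate matter. I assume 32 patients are enrolled to reach 24 completers, with half of the 8 drop-outs having scan 2.

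The 95% CI half-width for a mean change, in SD units, is t(0.975, n−1)/√n:
- n = 24 (completers): 0.422
- n = 28 (half of drop-outs have scan 2): 0.388
- n = 32 (all drop-outs have scan 2): 0.361

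The central case is a gain of 1 − 0.388/0.422 = 8%.

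For baseline correlations, the smallest |r| significant at two-sided 0.05 is t/√(n−2+t²), with t on n−2 df: 0.404 at n = 24 and 0.349 at n = 32.

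Over other assumed drop-out rates, 24 completers need 27, 30, 35 or 40 enrolled at 10%, 20%, 30% or 40%. If all of these had scan 2, the half-width would be 0.40, 0.37, 0.34 or 0.32 SD.

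**3. Bias, as illustration only**

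All inputs are assumed: half of patients respond; the 12-week change is −40% in responders and +10% in the rest; the scan-2 change is 70% of that (−28% and +7%); drop-out is 10% in responders and 40% in the rest; half of drop-outs have scan 2.
- Completers as a share of starters: 0.5 × 0.9 = 0.45 and 0.5 × 0.6 = 0.30.
- 12 weeks, completers: (0.45 × −40 + 0.30 × 10)/0.75 = −20.0%. All starters: 0.5 × −40 + 0.5 × 10 = −15.0%. The gap is 5.0 points.
- Scan 2, completers: (0.45 × −28 + 0.30 × 7)/0.75 = −14.0%. All with scan 2: (0.475 × −28 + 0.40 × 7)/0.875 = −12.0%. All starters: −10.5%.
- Drop-out reversed (40% and 10%): 12-week completer mean (0.30 × −40 + 0.45 × 10)/0.75 = −10.0%, which understates the fall.
- Drop-out 25% in both groups: −15.0%, no bias.

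**4. What a two-visit mixed model recovers in the 10%/40% case**

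In large samples the 12-week estimate is −20.0 + b × (−12.0 + 14.0) = −20.0 + 2b, where b is the slope of 12-week on scan-2 change among completers. Responders are 0.45/0.75 = 0.6 of completers, so b = (ρ·SD² + 0.24 × 35 × 50)/(SD² + 0.24 × 35²) = (ρ·SD² + 420)/(SD² + 294), with SD and ρ the assumed within-group SD and between-visit correlation.
- SD 10, ρ 0.7: b = 490/394 = 1.244; estimate −17.51; 2.51 points of bias remain.
- SD 25, ρ 0.7: b = 857.5/919 = 0.933; estimate −18.13; 3.13 remain. A simulation recruiting to 24 completers gave −18.2.
- SD 40, ρ 0.3: b = 900/1894 = 0.475; estimate −19.05; 4.05 remain.

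If no drop-out has scan 2, the model removes none of the 5.0 points.

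**The case against.** The best defence is that section 11.2 sets only the primary population, since the sentence after the restriction refers to the primary endpoint, and section 6 then covers everything else. The aim in section 3.2 is longitudinal change at baseline, 4-6 weeks and 12 weeks, so requiring three scans for that endpoint is coherent. In an exploratory, non-randomised study, change in completers is a legitimate descriptive target. Replacement protects the planned 24, so no planned precision is lost.

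Much of this stands. Completers are worth reporting and 24 is safe. However, the sentence restricts the data analysis as a whole. Even on the narrower reading, the primary change is confined to completers although baseline plus scan 2 meets the stated reason.

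A reader might infer more than the documents support:
- **That early leavers' scans are certain to go unused**, so that up to 2 × 11.7 = 23.4 mSv (section 9.3 maximum) was given for nothing. Section 6 says the data will be used where possible, and the uptake review after 5 cases in section 11.2 is not limited to completers.
- **That section 8.2 contradicts section 11.2.** Its passage on withdrawal mainly concerns documentation and is weak support. Its value here is that it foresees incomplete scan sets.
- **That staying on therapy is definitely a condition.** The literal wording says so, but 12 (±4) weeks is also the scan-3 window and may only describe the schedule. Read literally, a patient who stops after scan 2 and before about week 8 (12 − 4) but still has scan 3 counts towards the 24 and is not analysed.
- **That the completer mean overstates the fall in uptake.** Step 3 shows that it can overstate, understate or be unbiased.

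**Conclusion.** The point holds and should be fixed. Two parts need no assumed number: section 11.2 conflicts with section 6, and its stated reason covers neither the 4-6-week change in patients with scans 1 and 2 nor the objectives that can use the baseline scan alone.

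The consequence for the primary result is conditional. It is the change in patients who completed the scans and, on the literal wording, stayed on therapy. It is biased for change following therapy only if stopping is related to uptake change, and the documents fix neither direction nor size.

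The precision gain is modest: 8% of the half-width in the central case, resting on an assumed drop-out count. The 5.0-point bias, and the 2.51 to 4.05 points left after a mixed model (SD 10-40, correlation 0.3-0.7, half of drop-outs with scan 2), are illustrations and should not be read as estimates for this trial.

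**What to change.** Rewrite section 11.2 as follows:
- Analyse scan-2 change in all patients with analysable baseline and scan 2, and scan-3 change in all with analysable baseline and scan 3. A repeated-measures mixed model, valid under missing-at-random, is an optional way to combine them.
- Analyse healthy tissue against tumour at baseline, and baseline uptake against TMB and carnitine, in all patients with an analysable baseline scan.
- Keep three-scan completers as a sensitivity analysis, labelled as such.
- Report all injected patients, with reasons for missing scans.
- Keep the recruitment target of 24 with three analysable scans.

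Reconcile sections 5.1, 6, 8.1, 8.2 and 11.2 so that complete, evaluable and analysed each have one definition, and say whether therapy duration is part of any of them. This concerns who is analysed; it proposes no change to who is scanned or treated.

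The cost is wording and slightly more analysis work, with no extra scans. The primary estimate would then include patients who left early, so it answers a somewhat different question from the completer result. Any bias is reduced, not removed, and patients with only a baseline scan still contribute no measured change.

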3.2 Rationale

Hypothesis: Import of [¹⁸F]FPIA-detectable SCFA into tumours is high and decreases with effective treatment.

Aim: To investigate longitudinal changes in [¹⁸F]FPIA uptake at baseline, and at 4-6 weeks (1-2 cycles) and 12 weeks (± 4 weeks); (routine CECT evaluation timepoints) following treatment initiation in patients using TKIs, chemotherapy, IO, or combinations of these.

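### Does leaving the primary uptake metric, post-therapy scan and lesion summary open in section 11.2 undermine the estimate of change?

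*Combined protocol and SAP*

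**What the plan says.** Section 4.1 sets the primary objective as the magnitude of change in tracer uptake after therapy. Its endpoint is a "Quantitative longitudinal measurement of" uptake in metastatic renal cell cancer.

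The aim in section 3.2 is to follow "uptake at baseline, and at 4-6 weeks (1-2 cycles) and 12 weeks (± 4 weeks"), and section 5.1 schedules scans 2 and 3 accordingly. Section 5.1 counts a patient's data as complete only when all three scans can be analysed.

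Section 11.2 restricts the analysis to completed cases because the change in uptake "from baseline is measured based on the PET/CT scans pre- and post- therapy". It says that imaging is quantified by SUV and adds: "These may include SUVmean (mean of standardized uptake values (SUV) within an ROI) normalised to body weight (bw), SUVmax and SUVpeak", with tumour to background ratio as a further possibility. On lesions it says: "The whole body scans will provide response information (change in SUV) on non-target and target lesions combined". It also states: "An early stage review of tracer uptake after 5 cases will be carried out".

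Section 11.1 adds a general rule: "Statistical tests will use a 0.05 significance level and will be 2-sided unless otherwise noted". It ties no test to the primary endpoint. The synopsis labels the study an explorative biomarker investigation as well as Phase 2, and section 11.1 notes that the tracer has not been used in this disease before.

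**The concern.** Three elements of the main result are not pinned down:

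- **Metric.** The list of uptake parameters is permissive, and none is marked as primary.
- **Scan.** There are two post-therapy scans, and the endpoint wording does not choose between them.
- **Per-patient value.** Target and non-target lesions are pooled, but no rule says whether by mean, sum or hottest lesion, whether the lesion list is fixed at baseline, or whether liver and sub-1-cm lesions count as non-target.

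Four metrics and two scans give 8 candidate answers. Section 3.2 hypothesises that uptake "into tumours is high and decreases with effective treatment", so a reader may fear that the largest fall will be chosen. The reported change would then be exaggerated and its confidence interval would cover too rarely. If p-values guided the choice, the 5% error rate would not hold. The review after 5 cases seems to add an early look at the data before anything is fixed.

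**Working it through.** **Inputs.** From the documents: n = 24 evaluable patients; 3 SUV metrics, or 4 if tumour to background ratio is counted; 2 post-therapy scans. The documents give no effect size, no SD of change and no correlation between metrics. I assume equal true change and SD for every metric, and a common between-metric correlation r of 0.8 to 0.95. The metrics come from the same regions on the same images, so high correlation is plausible, but it remains an assumption.

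**The plan's own figure.** There is none to reproduce for change. The sample size of 24 is tied to an upper confidence limit for sensitivity, which does not concern change, so 24 serves here only as n.

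**Step 1: precision with one pre-named analysis.** The 95% half-width is t(0.975, 23)/√24 = 0.42 SD.

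**Step 2: which choices are really open?** Set the passages side by side. The endpoint is longitudinal (4.1), the aim covers both time points (3.2), a complete case has all three scans (5.1), and the secondary objective in 4.2 again uses both times. The pre- and post-therapy wording in 11.2 fits either scan. The natural reading is that change is reported at each scan. The scan then stops being a choice, and what remains to count is the metric.

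**Step 3: shift from picking the largest fall among k metrics at one scan.** For k equally correlated normal results with no true change, the mean of the largest fall is

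shift = c(k) × √((1 − r)/n), in SD units,

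where c(k) is the expected maximum of k independent standard normals: c(3) = 0.846, c(4) = 1.029.

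| k | r | Calculation | Shift (SD) | Simulated coverage of nominal 95% CI |
|---|---|---|---|---|
| 3 | 0.80 | 0.846 × √(0.20/24) | 0.077 | 94.4% |
| 3 | 0.95 | 0.846 × √(0.05/24) | 0.039 | 94.8% |
| 4 | 0.80 | 1.029 × √(0.20/24) | 0.094 | 93.9% |
| 4 | 0.95 | 1.029 × √(0.05/24) | 0.047 | 94.7% |

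Coverage comes from 200,000 simulated studies per row, with a one-sample t interval around the selected metric. The simulated shifts agree with the formula to within 0.001 SD.

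**Step 4: what this means in percent.** If the SD of the per-patient log ratio is 0.2 to 0.5 (assumed), a true change of 0% would read as exp(−0.039 × 0.2) − 1 = −0.8% at one end and exp(−0.094 × 0.5) − 1 = −4.6% at the other.

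**Step 5: the pessimistic reading.** If one result could be picked from 4 metrics × 2 scans = 8, with metric correlations 0.8 to 0.95 and scan correlations 0.5 to 0.7, the shift is 0.11 to 0.17 SD and coverage 90 to 93%. At least one two-sided p < 0.05 would occur by chance in about 13 to 21% of studies. These figures require setting aside the two-time-point aim and then reporting only the best result. The error rate also requires a test that the plan never attaches to the primary endpoint.

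**The case for a change.** The strongest reply is that an estimate needs a definition even in exploratory work. The magnitude of change is the primary objective, the study is also called Phase 2, and tests at 0.05 are foreseen. Naming one metric needs no prior uptake data, would cost a sentence, and would leave the others as supportive results. If longitudinal means that all scans are used, one would still expect a stated summary. Unstated lesion rules add choices that the calculation above does not count.

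Part of this stands. The metric and the lesion-combining rule are unstated, and no other section supplies them. Settling them before the final analysis is good practice. The pooled lesion set is at least named, which leaves only the arithmetic of pooling open. The question about liver and small lesions is fair but minor, since the 1 cm and non-liver condition in section 6.3 is an entry criterion and does not define non-target disease.

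Other parts are weaker. The 5-case review concerns tracer uptake and may rest on baseline scans alone; it is not described as a look at change. Nor is a larger average fall plainly the favoured result. The hypothesis ties a fall to effective treatment, patients receive mixed therapies, and the secondary objective sets changes against routine imaging. Finally, section 11 plans no confidence interval for change, so lost coverage concerns an interval the analysts would be adding themselves.

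**Conclusion.** No change to the plan is needed. Section 11.2 is incomplete on the headline metric and the lesion summary, and ambiguous rather than silent on the scan. Nothing it states leads to a wrong result: reporting the listed SUV parameters at both post-therapy scans gives a sound description for a first-use, exploratory study. Harm arises only if analysts report nothing but the largest fall, which the plan does not propose. Even then, selection among metrics at a given scan moves the mean by about 0.04 to 0.09 SD, at most about a fifth of the 0.42 SD half-width (0.094/0.42 = 0.22), and leaves coverage at about 94 to 95%. This conclusion rests on reading the endpoint as covering both scans and on assumed metric correlations of 0.8 to 0.95. Lower correlations, or free choice among lesion summaries, would enlarge the conditional risk. A fixed log-SUVmax summary, Holm's procedure over scans or a separate rule for new lesions would be reasonable preferences, but they would fill a gap rather than correct an error.

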12 REGULATORY, ETHICAL AND LEGAL ISSUES

12.1 Good Clinical Practice

The study will be conducted in accordance with the guidelines laid down by the International Conference on Harmonisation for Good Clinical Practice (ICH GCP E6 guidelines).

12.2 Ethics Approval

The Study Coordination Centre has obtained approval from the West of Scotland Research Ethics Committee (REC) 5 and Health Regulator Authority (HRA). The study must also receive confirmation of capacity and capability from each participating NHS Trust before accepting participants into the study or any research activity is carried out. The

study will be conducted in accordance with the recommendations for physicians involved in research on human subjects adopted by the 18th World Medical Assembly, Helsinki 1964 and later revisions.

